- To assess feasibility of the simultaneous insertion of coated and uncoated ETT, CVC and UC in recently admitted critically ill patients without previous invasive devices in a randomized controlled trial.
- To determine how many patients admitted to the ICU will require CVC, ET and UC insertion and, of those, how many will develop sepsis from 48 hours after randomization until day 28 after randomization or until ICU discharge.

Secondary objectives (clinical outcomes):

- Occurrence of nosocomial sepsis up to 28 days after randomization in control (uncoated devices) versus intervention (coated devices) groups
- Combined endpoint of any of the following infections occurring during ICU stay: Ventilator associated pneumonia (VAP), Catheter related bloodstream infection (CRBSI) and Catheter associated urinary tract infection (CAUTI).
- Occurrence of each nosocomial infection individually (VAP, CRBSI, CAUTI) in both groups and rates of positives cultures at each site.
- ICU and Hospital mortality in both groups.

3. Study methods

The full methods section, including detailed intervention and eligibility (inclusion and exclusion criteria), is explained in the Protocol.

3.1) Trial design

Pilot exploratory, randomized, open label, controlled trial. Critically ill patients which will demand placement of invasive devices for organ support (endotracheal tube, central venous catheter and urinary Foley catheter) will be randomized 1:1 to receive coated (Bactiguard®) or habitual (non-coated) devices.

3.2) Method of randomization and concealment allocation

Randomization list will be electronic generated using appropriate software and will be done in blocks stratified by site and by the presence of sepsis at randomization. Allocation group will only be informed after patient register in the electronic database, thereby preventing the investigator of anticipating for which group the patient will be randomized. Due to technical reasons, there will be no blinding.

3.3) Outcomes

The analysis of the two main outcomes involves both the feasibility of the study and the need to obtain epidemiological data on the occurrence of nosocomial sepsis after ICU admission. The feasibility will be assessed by study recruitment rate and by local input on the challenges of the randomization process. We expect a recruitment rate of approximately 1.3 patients a month per site.

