Sepsis will be defined as the occurrence of infection plus presence of organ failure, assessed by the Sequential Organ Failure Assessment (SOFA) score (Singer, JAMA 2016; Vincent, Intensive Care Med 1996). The presence of infection with an increase in SOFA score in at least two points will be considered as sepsis (Singer,

JAMA 2016). Sepsis will be further classified as probably related to devices or non-related to the devices after adjudication. Sepsis non-related to the devices will be those where an obvious source of infection that is not related to the devices and is present at device insertion or when the time between device insertion and sepsis diagnosis is less than 48 hours. Obvious sepsis sources unrelated to the devices include: Meningitis, soft tissue infections away from the puncture site (i.e., necrotizing fasciitis), intrabdominal infection and surgical wound infection. An introduction of a new antibiotic class will be used to trigger investigation.

VAP will be defined considering the classic diagnostic criteria (Kalanuria, Crit Care 2014):

1. New or progressive radiographic consolidation or infiltrate. In addition, at least 2 of the following:
 - a. Temperature $> 38^{\circ}\text{C}$
 - b. Leukocytosis (white blood cell count $\geq 12,000 \text{ cells/mm}^3$) or leukopenia (white blood cell count $< 4,000 \text{ cells/mm}^3$)
 - c. Presence of purulent secretions

CRBSI will be defined if **one** of the following is present plus criteria for identifying the catheter as the source (ECDC, 2013):

1. Patient has a recognized pathogen cultured from one or more blood cultures, and the pathogen is not related to an infection at another site.

OR

2. Patient has at least one of the following signs or symptoms: fever ($>38.0^{\circ}\text{C}$), chills, or hypotension, and the pathogen is not related to an infection at another site or, if the organism is a common commensal, it must be present from two or more blood cultures drawn on separate occasions. **AND**

3. Culture of the same organism from both the catheter tip and at least one percutaneous blood culture
4. Culture of the same organism from at least two blood samples (one from a catheter hub and the other from a peripheral vein or second lumen) meeting criteria for quantitative blood cultures (at least 5 times greater in

7(13)

catheter blood) or differential time to positivity (at least 2 hours earlier in catheter blood).

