Therefore, for CRBSI to be diagnosed, patient must have criteria 1 OR 2 plus 3 OR 4.

Finally, CAUTI will be defined if **all** the following are present (Nicolle, Antimicrob Resist Infect Control 2014):

1. One or more organisms are present at quantitative counts $\geq 10^5$ colony-forming units/mL from an appropriately collected urine specimen
2. The attending physician believes there is an acute infection and prescribes antibiotics
3. There is no other plausible source of infection at the time the diagnosis of CAUTI is made

The number of antibiotic free days at 28 days will be defined as 28 less the number of days the patient received antibiotics.

All events will be adjudicated by the coordinating center.

3.4) Sample size

This is a pilot study including 100 unique patients. The density of incidence of sepsis and other device-related infection (VAP, CRBSI and CAUTI) will be calculated as the number of events over the total number of patients/day at risk. For the primary outcome of incidence of sepsis, this sample size will be able to inform 95% credible intervals with approximately 3 events per 100 patient-days overall (4 events per patient-day per group), and interval length based on Bayesian *Poisson* regression model with intercept parameter assuming non-informative normal prior centered in 8 event per 100 patient-days incidence rate, $N(e^{0.08}, 5)$.

The prior has a very large standard deviation, giving virtually no importance to its average choice, which was established assuming a slightly worse scenario than was described for a European population of 5 events per 100 patient-days (Allegranzi, 2011).

4. Analyses set

Study protocol mentioned that analysis will be done considering the intention to treat principle. However, during study conduction, some randomized patients did not require simultaneous insertion of all three devices (ETT, CVC and UC) due to illness severity, or the attending physician decided not to insert the devices. Those cases were excluded from the analyses. Consequently, main analysis will be carried out considering a Per Protocol Set (PPS) above. Our expectations are that per protocol and full compliance sets will be the same. Nevertheless, if it happens otherwise, full compliance set must be used to evaluate efficacy measures (infection incidences) and per protocol set to evaluate security measures (adverse events).

4.1) Per Protocol Set

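### The VAP and CAUTI criteria set no minimum time after device insertion and do not exclude infection already present, so admission pneumonia or urinary infection can be counted as device infection

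*SAP*

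**What the plan says.** **VAP (section 3.3).** The criteria are "New or progressive radiographic consolidation or infiltrate. In addition, at least 2 of the following": fever, abnormal white count, purulent secretions. No ventilation or tube time is given.

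**CAUTI (section 3.3).** Three conditions must all hold: a quantitative urine count of at least 10^5 CFU/mL; "The attending physician believes there is an acute infection and prescribes antibiotics"; and "There is no other plausible source of infection at the time the diagnosis of CAUTI is made". No catheter time is given.

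**CRBSI (section 3.3).** No catheter time is given here either, but the source must be shown: "Therefore, for CRBSI to be diagnosed, patient must have criteria 1 OR 2 plus 3 OR 4". Criteria 3 and 4 are culture proof from the catheter tip or from paired samples. Criteria 1 and 2 contain the condition that "the pathogen is not related to an infection at another site".

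**Window (section 2.1).** The composite is described as "Combined endpoint of any of the following infections occurring during ICU stay", with no start offset. The separate infections are listed as "Occurrence of each nosocomial infection individually (VAP, CRBSI, CAUTI) in both groups", with no window stated.

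**Sepsis.** The primary objective (section 2.1) starts counting sepsis 48 hours after randomization. Section 3.3 classes sepsis as unrelated to the devices "when the time between device insertion and sepsis diagnosis is less than 48 hours".

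**Other relevant text.** Randomization is stratified by sepsis at randomization (section 3.2). The coordinating center adjudicates all events (section 3.3). Section 3.4 groups VAP, CRBSI and CAUTI as device-related infections and divides events by patient-days at risk. Section 5.3 reports both adjudicated and center-reported events and uses the models to simulate a larger trial.

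**The concern.** VAP and CAUTI are meant to capture infection acquired on the device. The printed criteria establish that pneumonia or urinary infection is present, but not that it arose after the device went in. Stratifying on sepsis at randomization means that infected patients are enrolled by design, so infection at entry is to be expected.

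A coating cannot prevent an infection that precedes it. Each such event raises the infection rate in both arms and adds a comparison with a true ratio of 1, so the coated-versus-habitual RR moves towards 1. Adjusting for sepsis at randomization (section 5.3) does not undo this, because the events stay in the counts. Both the inflated rate and the diluted ratio would then feed the simulations for the larger trial, which is a main use of a pilot. Admission infections should also concentrate in the sepsis stratum, so uneven dilution could look like an interaction in the one planned subgroup analysis (section 5.5).

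**Working it through.** The plan gives no figure on this point to reproduce. The check has a textual part and an illustration.

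**1. Time rules, endpoint by endpoint**

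| Endpoint | Minimum time after insertion | Excludes infection present at insertion | Other protection |
|---|---|---|---|
| Sepsis | 48 h for device-relatedness; 48 h after randomization for the primary window | Yes, an obvious unrelated source is classed as non-device | Adjudication |
| VAP | None | No | Infiltrate must be new or progressive; adjudication |
| CAUTI | None | No | No other plausible source; adjudication |
| CRBSI | None | Not by time | Culture proof of the catheter as source; pathogen not from another site; adjudication |
| Composite | None; ICU stay | No | As for its components |

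**2. Two cases run through the printed criteria**

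- *Patient intubated for pneumonia.* A new infiltrate, fever and leukocytosis satisfy the VAP criteria on the day of intubation. If SOFA rises by two points 6 hours after intubation, section 3.3 classes the sepsis as not device-related, while the same pneumonia meets the VAP definition.
- *Patient admitted with urosepsis.* A count of at least 10^5 CFU/mL, a physician's diagnosis with antibiotics, and no other source satisfy all three CAUTI conditions on the day of catheterization. The clause on other sources does not help, because the urinary tract is the source.

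**3. Illustration of size**

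Assumed, not in the SAP: 50 patients per arm (100 randomized 1:1), equal patient-days per arm, *a* true device infections on coated and *b* on habitual devices, and *m* admission infections counted in each arm.

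Observed RR = (a + m) / (b + m)

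| True events (coated v habitual) | True RR | m = 4 | m = 8 |
|---|---|---|---|
| 7 v 10 | 0.70 | 11/14 = 0.79 | 15/18 = 0.83 |
| 5 v 8 | 0.63 | 9/12 = 0.75 | 13/16 = 0.81 |

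In the first row, the habitual-arm count rises from 10 to 14 (+40%) or 18 (+80%).

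**4. The same effect as a share of events**

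Let *s* be the share of counted habitual-arm events that were present at insertion. Then observed RR = s + (1 − s) × RR. With an assumed true RR of 0.60, and events for a later trial by the Schoenfeld formula (two-sided 0.05, 80% power, 1:1):

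| s | Observed RR | Events needed |
|---|---|---|
| 0% | 0.60 | 121 |
| 10% | 0.10 + 0.90 × 0.60 = 0.64 | 158 |
| 20% | 0.20 + 0.80 × 0.60 = 0.68 | 212 |
| 30% | 0.30 + 0.70 × 0.60 = 0.72 | 291 |
| 40% | 0.40 + 0.60 × 0.60 = 0.76 | 417 |

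The direction is certain whenever *s* is above 0 and the true RR is below 1. The size depends entirely on *s*, which the SAP does not allow one to estimate.

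**The case against.** The best defence is that the criteria should be read with the terms around them. The outcomes are called ventilator-associated, catheter-associated, nosocomial and device-related, and they are analysed as incidence over time at risk. A pneumonia that led to intubation is none of these, and adjudicators would presumably reject it. The protocol, or the sources cited for the definitions, may also carry a time threshold.

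Part of this stands. Those words and adjudication will probably remove some admission infections, so not every such event would be counted. What does not stand is that they settle the matter. None states an hour count, adjudicators receive no timing rule for these infections, the trial is open label, and center-reported events are also presented. The protocol was not available for this review, so the gap is shown for the SAP only. But the SAP prints the criteria in full and states 48 hours for sepsis alone.

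A reader might also infer more than the text supports:

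- *That all three infections are equally exposed.* CRBSI lacks a time rule too, but it needs culture proof of the catheter as source and a pathogen not explained by another site. An infection that precedes the line cannot readily meet that.
- *That all three are counted over the whole ICU stay.* Only the composite has that window; the separate infections have none stated.
- *That the SAP contradicts itself.* The 48-hour statements concern sepsis. Not extending them is an inconsistency; no two statements conflict.
- *That the primary outcome is affected.* The primary sepsis window already starts at 48 hours. The planned subgroup analysis will also show patients without sepsis at entry, in whom the problem should be smallest.

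**Conclusion.** The point holds for VAP, CAUTI and the composite. Followed as printed, the criteria let pneumonia or urinary infection present at insertion count as a device infection, and this is out of line with the SAP's own handling of sepsis. It concerns secondary and exploratory outcomes of a 100-patient pilot. It matters mainly for the infection rates and the RR carried into planning of the larger trial.

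The size is unknown. The shift from 0.70 to between 0.79 and 0.83 rests on assumed event counts, on 4 to 8 admission infections per arm, and on all of them being accepted. It illustrates the mechanism and is not an estimate for this trial. Adjudicated results are likely to be less affected than center-reported ones. If the protocol already states an onset rule, the remaining problem is that the SAP neither repeats it nor refers to it.

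**What to change.** In section 3.3, align the VAP and CAUTI definitions with the SAP's existing 48-hour rule, and do the same for CRBSI for consistency:

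- onset at least 48 hours after insertion of the corresponding device;
- the device in place at onset, or removed within a stated short period before it;
- infection not present at insertion.

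Give the composite in section 2.1 the same start, and state the window for the separate infections. In section 5.3, say that the rule applies to both adjudicated and center-reported events. If the protocol already has such a rule, cite it.

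The change is SAP wording plus the use of insertion and event dates. It gives fewer countable events, in proportion to the admission infections removed. On the assumed figures, the habitual arm would fall from 14 to 10 (4/14 = 29%) or from 18 to 10 (8/18 = 44%). The events lost are ones that the coating could not have prevented.

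### CRBSI criterion 2 joins its two safeguards with 'or', so no reading of it applies both the other-site exclusion and the two-culture rule to a common commensal

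*SAP*

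**What the plan says.** SAP section 3.3 builds the CRBSI definition from four numbered criteria.

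- Criterion 1 covers a recognised pathogen "cultured from one or more blood cultures, and the pathogen is not related to an infection at another site". The other-site exclusion is attached with *and*.
- Criterion 2 opens with "Patient has at least one of the following signs or symptoms: fever" (above 38.0 °C), chills or hypotension. It then requires that "the pathogen is not related to an infection at another site or, if the organism is a common commensal, it must be present from two" cultures at minimum; the full wording of the count and timing is "two or more blood cultures drawn on separate occasions". Here the other-site exclusion and the commensal rule are linked by *or*.
- Criterion 3 is "Culture of the same organism from both the catheter tip and at least one percutaneous blood culture".
- Criterion 4 begins "Culture of the same organism from at least two blood samples (one from a catheter hub and the other from a peripheral vein"; a second lumen may take the place of the vein. It adds a quantitative ratio of at least 5 or a lead of at least 2 hours in the catheter sample.

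The section then sums up: "Therefore, for CRBSI to be diagnosed, patient must have criteria 1 OR 2 plus 3 OR 4". It adds that the coordinating center adjudicates all events. No other part of the SAP restates or corrects criterion 2.

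**The concern.** A commensal in a blood culture raises two separate doubts: it may be a contaminant, and it may have come from somewhere other than the catheter. Criterion 2 contains a safeguard against each, but the connector makes them alternatives.

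The SAP's own wording suggests that both were meant as requirements. Criterion 1 attaches the same other-site exclusion with *and*, and criterion 2 says that a commensal *must* appear in two or more cultures. This is an inference from the text. The surveillance definition that the SAP cites is not at hand and plays no part in it.

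CRBSI is a listed secondary outcome and a component of the combined endpoint (section 2.1). Section 5.3 models its incidence, compares it between coated and habitual devices, and uses the models to simulate a larger trial. In an open-label pilot of 100 patients, an infection rule that can be read in more than one way should be settled before events are classified.

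**Working it through.** The SAP gives no figure to reproduce on this point, so the check is a truth table of criterion 2.

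**Inputs, all from section 3.3**
- S: at least one listed sign or symptom. It is taken as true throughout.
- N: the organism is not related to an infection at another site.
- C: the organism is a common commensal.
- T: it is present in two or more blood cultures on separate occasions.

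**Readings of the sentence**
- A, literal *or*: S and (N or (C and T)).
- A2, literal *or* with the *if* as a logical conditional: S and (N or (not C or T)).
- B, split by organism, so that *must* acts as a separate rule for commensals: S and ((not C and N) or (C and T)).
- Both required: S and N and (not C or T).

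**Result for the four commensal patterns (C true)**

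| N | T | A | A2 | B | Both required |
|---|---|---|---|---|---|
| yes | yes | met | met | met | met |
| yes | no | **met** | **met** | not met | not met |
| no | yes | **met** | **met** | **met** | not met |
| no | no | not met | not met | not met | not met |

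Against the rule that requires both safeguards, A and A2 each admit 2 of the 4 commensal patterns wrongly, and B admits 1 of 4. The third row, a commensal in two or more cultures that is related to another site, is admitted under all three. The second row, a single-culture commensal with no other source, is admitted only when the *or* is taken literally. Attaching the symptom requirement to the first limb only, (S and N) or (C and T), gives the same column as A when S is true.

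For non-commensals, A and B agree with the both-required rule. Only A2 also admits a non-commensal related to another site.

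**Do the later criteria repair this?** Meeting criterion 2 is not yet CRBSI, because criterion 3 or 4 must also be met.
- Single-culture commensal: criterion 3 accepts the catheter tip plus one percutaneous culture, so under the literal reading this case can become a CRBSI. Criterion 4 needs two samples but not separate occasions.
- Two-culture commensal from another site: neither criterion 3 nor criterion 4 repeats the other-site exclusion, so this case can pass, for instance with a secondarily colonised tip.

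**Does adjudication repair it?** All events are adjudicated, but the SAP gives adjudicators no other rule for commensals. Section 5.3 also reports results for events as reported by the centers, and it supplies a separate center-reported definition for sepsis only.

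**The case against.** The strongest reply is that the organism-split reading is the natural one. Criterion 1 already admits a recognised pathogen not related to another site, without symptoms, so the main independent work of criterion 2 concerns commensals. For those the text says *must*, and a literal *or* would empty that word of effect. This stands: on the natural reading, the single-culture commensal fails criterion 2.

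A second reply is that criteria 3 and 4 demand positive evidence of catheter origin: the same organism on the tip, or a quantitative or time-to-positivity difference. A commensal from another site that passes them should be uncommon, and adjudication gives a further check. This also stands as a limit on the effect, but it narrows the gap without closing it.

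A third is that the intended rule is inferred. That is so. The *and* in criterion 1 supports the inference but does not prove that the other-site exclusion was meant to cover commensals.

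A reader might go further and infer that contaminated single cultures will inflate CRBSI by a substantial, calculable fraction. The SAP does not support this. That harm exists only under the literal *or*. Any figure would need contamination rates, numbers of cultures, tip-match rates and a true CRBSI rate, none of which the SAP gives. It would also say nothing about the other-site case, which is the part that holds on every reading.

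**Conclusion.** The point holds as a drafting error in an outcome definition. No reading of criterion 2 applies both safeguards to a common commensal. The other-site gap is present on every reading; the single-culture gap depends on taking the *or* literally. The conclusion assumes that both safeguards were meant as requirements and that a common commensal enters through criterion 2, not as a recognised pathogen under criterion 1.

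The consequence is possible misclassification in the CRBSI and combined-endpoint counts and, through section 5.3, in the CRBSI comparison between arms. How many events are affected cannot be worked out from the SAP. The primary sepsis outcome is not at issue: section 3.3 defines it by infection plus a rise in SOFA, without calling on the CRBSI criteria. This is a minor but worthwhile correction.

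**What to change.** Rewrite criterion 2 as three joined requirements: (a) at least one of temperature above 38.0 °C, chills or hypotension; AND (b) the organism is not attributable to infection elsewhere; AND (c) where it is a common commensal, it grows in at least two blood cultures taken on different occasions. Write the overall rule with brackets: (1 OR 2) AND (3 OR 4). If the alternatives were in fact intended, the SAP should say so and state which safeguard applies to which organism.

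With requirements (a) to (c), a commensal in two cultures with no other source still qualifies, while the two disputed patterns fail criterion 2. The cost is one sentence of SAP wording, a second look at the few commensal cases at adjudication, and possibly slightly fewer CRBSI events.

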All patients that were randomized, fulfill all inclusion and exclusion criteria, and receive the three devices (ETT, CVC and UC) from allocated arm (coated or habitual) at least one time.

4.2) Full compliance set

All patients that were randomized, fulfill all inclusion and exclusion criteria, and receive the three devices (ETT, CVC and UC) from allocated arm (coated or habitual) all the times that were needed.

5. Analyses Methods

Continuous data will be reported as mean (standard deviation) or median (quartiles) as appropriate. Categorical variables will be described by absolute and relative frequencies.

5.1) Baseline characteristics

Patients' baseline characteristics will be presented without any hypothesis test comparing patients allocated to Coated versus Habitual devices.

5.2) Primary outcome

As described at section 3.4 (sample size), the primary outcome of incidence of sepsis, will be estimated via Bayesian *Poisson* regression model with intercept parameter assuming non-informative normal prior centered in 8 event per 100 patient-day incidence rate, $N(e^{0.08}, 5)$.

5.3) Exploratory outcomes

The same Bayesian *Poisson* regression model with intercept parameter assuming non-informative normal prior centered in 8 event per 100 patient-day incidence rate, $N(e^{0.08}, 5)$, will be done to estimate other infection incidences (VAP, CRBSI, CAUTI).

Besides, the same model will be used to compare patients that used coated devices versus habitual devices. Results will be reported as Risk Ratios (RR) with 95% Credible Intervals. Models will be adjusted for admission type, baseline SOFA and the stratification variable (presence of sepsis at randomization).

Results will be reported considering adjudicated events and events reported by the centers. Sepsis, as reported by centers will be considered as: two point increase in SOFA plus newest use of ATB. The end of sepsis will be considered at the time of ATB withdrawal concomitant with any improvement in SOFA.

Based on those models, we will run simulations to explore scenarios for a larger trial.

5.4) SOFA

We intent to evaluate SOFA during ICU stay using hierarchical Bayesian linear regression models assuming intercept and slope hierarchical effects to patient to include individual time dependence, adjusted for baseline SOFA, and interaction of time and allocated device (coated or habitual). All priors shall be non-informative Normal distributed.

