We may also test some nonlinear relation of SOFA on time in each group using polynomial or natural cubic splines. And evaluate alternatives to control death censoring (REF - <http://dx.doi.org/10.1136/bmj.j5748>) if mortality seems different between arms.

Results will be presented with proper graphs to highlight SOFA variation on time.

5.5) Subgroup analysis

Subgroup analysis will be tested by including interaction effect parameter into the model previously described in section 5.3. The only planned subgroup variable is the stratification characteristic: presence/absence of sepsis at admission.

5.6) Safety and Adverse Events

All reported Safety and Adverse events as described in the protocol will be presented with absolute and relative frequencies and tested with regular Fisher exact test between study groups (Coated vs. Habitual devices).

5.7) Missing data and imputation

We expect minimal missing data; none data imputation is planned.

6. Statistical software

Analyses will be done using R software (R Core Team, 2019). Bayesian models will be adjusted using *rstan* package (Stan Development Team, 2019).

REFERENCES

Nicolle LE. Catheter associated urinary tract infections. *Antimicrob Resist Infect Control*. 2014 Jul 25;3:23

Stan Development Team (2019). RStan: the R interface to Stan. R package version 2.19.2. <http://mc-stan.org/>.

R Core Team (2019). R: A language and environment for statistical computing. R Foundation for Statistical Computing, Vienna, Austria. URL <https://www.R-project.org/>.

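### Antibiotic-free days are 28 minus antibiotic days with no term for death, so days after death count as antibiotic-free (low weight: the outcome is unlisted and unmodelled)

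*SAP*

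**What the plan says.** Section 3.3 (Outcomes) defines the score in full: "The number of antibiotic free days at 28 days will be defined as 28 less the number of days the patient received antibiotics". Death and discharge before day 28 are not mentioned.

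Other parts of the SAP that bear on it:

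- Section 2.1 does not list the score among the primary or secondary objectives. It does list "ICU and Hospital mortality in both groups", so deaths are expected. It follows sepsis "until day 28 after randomization or until ICU discharge".
- Sections 5.2 to 5.5 give the score no model. The models in section 5.3 are for infection incidences. What remains is the general rule in section 5: "Continuous data will be reported as mean (standard deviation) or median (quartiles) as appropriate".
- Section 5.4 raises death as an analytic problem for SOFA, with a plan to "evaluate alternatives to control death censoring", and only "if mortality seems different between arms".
- Section 5.7 plans no imputation and does not mention death.

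**The concern.** A patient who has died receives no antibiotics, so the formula credits each remaining day to day 28 as antibiotic-free. Compared with the same patient surviving, death before day 28 can raise the score or leave it unchanged, but can never lower it. A score with this name will be read as higher is better, and on that reading an early death outranks a treated survivor.

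At stake is a descriptive comparison. If one arm has more or earlier deaths and antibiotic practice while alive is the same, that arm will tend to show more antibiotic-free days. With equal mortality and timing the arms stay comparable, but the level of both means is hard to interpret. The SAP does not predict a mortality difference, though section 5.4 allows for one.

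**Working it through.** The SAP states no expected value, power or sample size for this score, so there is no figure of its own to reproduce.

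**Single patients, as written.** Death on day 3 after 3 antibiotic days: 28 − 3 = 25. Survivor of a 10-day course: 28 − 10 = 18.

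**Level with equal mortality.** Assume 30% mortality, all deaths on day 3 on antibiotics, and survivors treated for 10 days. The mean as written is 0.7 × 18 + 0.3 × 25 = 20.1. With death scored 0 it is 0.7 × 18 = 12.6.

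**Difference between arms.** Let mortality be m1 and m2, with mean antibiotic days A_S in survivors and A_D in patients who die, the same in both arms. Then

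- shift as written = (m2 − m1) × (A_S − A_D);
- shift with death scored 0 = −(m2 − m1) × (28 − A_S).

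All inputs are assumptions. Antibiotics are given on 30, 45 or 60% of days alive, or as one course of 7, 10 or 14 days cut short by death. Deaths are uniform over days 1–7, 1–14 or 1–28 (mean day 4, 7.5 or 14.5). That makes 18 scenarios. At 30% versus 40% mortality, in days (positive favours the higher-mortality arm):

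| Antibiotic pattern | A_S | As written, deaths days 1–7 | Days 1–14 | Days 1–28 | Death scored 0 (any timing) |
|---|---|---|---|---|---|
| 30% of days | 8.4 | +0.72 | +0.62 | +0.41 | −1.96 |
| 45% of days | 12.6 | +1.08 | +0.92 | +0.61 | −1.54 |
| 60% of days | 16.8 | +1.44 | +1.23 | +0.81 | −1.12 |
| 7-day course | 7 | +0.30 | +0.15 | +0.08 | −2.10 |
| 10-day course | 10 | +0.60 | +0.32 | +0.16 | −1.80 |
| 14-day course | 14 | +1.00 | +0.65 | +0.33 | −1.40 |

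One cell in full (10-day course, deaths days 1–14): A_D = (1 + … + 10 + 4 × 10)/14 = 95/14 = 6.79, so a patient who dies scores 21.21 on average. The arm means are 0.7 × 18 + 0.3 × 21.21 = 18.96 and 0.6 × 18 + 0.4 × 21.21 = 19.29, a difference of +0.32 before rounding.

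At 30% versus 50% every entry doubles: +0.15 to +2.88 as written, −2.24 to −4.20 with death scored 0.

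**Timing alone.** With 30% mortality in both arms, deaths on days 1–7 in one and days 1–28 in the other, the earlier-death arm scores better by 0.3 × (difference in A_D). This is 0.95, 1.42 and 1.89 days for 30, 45 and 60% use, and 0.67, 1.32 and 2.02 days for 7-, 10- and 14-day courses.

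**Reversal.** In the 10-day-course cell, let the extra 10% die on day 20 after 20 antibiotic days, scoring 8. The mean is 0.6 × 18 + 0.3 × 21.21 + 0.1 × 8 = 17.96 against 18.96, so that arm is 1.0 day worse.

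**Against sampling error, largest scenario only** (60% use, deaths days 1–7, binomial antibiotic days). The SDs are 7.00, 7.40 and 7.51 at 30, 40 and 50% mortality.

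- 50 per arm: SE = √((7.00² + 7.40²)/50) = 1.44, ratio 1.44/1.44 = 1.0. At 30% versus 50%, SE 1.45, ratio 2.88/1.45 = 2.0.
- 40 per arm (assumed, since section 4 says of some randomised patients "Those cases were excluded from the analyses"): SE 1.61 and 1.62, ratios 0.9 and 1.8.

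**The case against.** The strongest reply is that the number is a coherent measure of antibiotic consumption, and that the SAP never says it will be read as benefit or compared between arms. It enters no objective, sample size, model or subgroup analysis in a 100-patient feasibility pilot. Mortality by arm is already a secondary outcome, so a reader would have it. The magnitudes rest wholly on assumed inputs: the median shift at 30% versus 40% is about 0.6 day, four of the nine fixed-course scenarios give 0.3 day or less, and the ratio of 2.0 standard errors is the worst corner of a 20-point mortality gap. The remedy also moves with mortality, and by more in most scenarios. The protocol, which is not shown, may list the outcome or say how death is handled.

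Most of this stands, and it limits the point to low weight. It does not remove it. The SAP writes out a complete rule, so this is not a detail left to the protocol, and nothing in the SAP ties mortality to this score. Patient-days at risk do shorten with death in the infection rates, but that does not touch this formula. Scoring death as 0 does shift more in 16 of 18 scenarios (the exceptions are 60% use with deaths on days 1–7 or 1–14). However, it shifts against the arm with more deaths, which is the direction the score's name implies.

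**Conclusion.** The concern holds, at low weight. Followed literally, the definition counts days after death as antibiotic-free; that needs no assumption. A between-arm distortion needs mortality or its timing to differ. With equal antibiotic practice, and under the assumed ranges, it is 0.1 to 1.4 days in favour of the higher-mortality arm at 30% versus 40%, 0.2 to 2.9 days at 30% versus 50%, and 0.7 to 2.0 days from timing alone. This is a tendency, not a rule: it holds when patients who die have had fewer antibiotic days than survivors, and reverses when the extra deaths follow long courses. No primary result depends on it.

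**What to change.** **If vital status and antibiotic use are known to day 28,** redefine the outcome in section 3.3 as days alive and free of antibiotics to day 28, with death by day 28 scored 0. Present mortality beside it. State that the score is then a composite that moves with mortality even when antibiotic practice is equal (1.1 to 2.1 days against the higher-mortality arm at 30% versus 40%).

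**If day-28 data are not collected after discharge,** do not count free days over the observed stay, because that rewards long stays: discharge on day 5 with no antibiotics scores 5, while a 28-day stay with a 10-day course scores 28 − 10 = 18. Report antibiotic days per 100 patient-days observed alive. At 30% versus 40% mortality this rate does not move when use is proportional to days alive, but rises by 1.4 to 2.7 per 100 with fixed courses. In the 10-day-course cell it is (0.7 × 10 + 0.3 × 6.79)/(0.7 × 28 + 0.3 × 7.5) = 41.4 per 100 against (0.6 × 10 + 0.4 × 6.79)/(0.6 × 28 + 0.4 × 7.5) = 44.0 per 100. The SAP should note this.

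**Cost.** A short change to one definition if the day-28 data exist, which the SAP does not show; otherwise a rate replaces the score. No model or sample size changes.
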